2 METHODOLOGY

2.1 STUDY DESIGN

This is a longitudinal, **randomized, comparative** interventional study of type 1 or 2 diabetic patients requiring insulin treatment delivered by a patch pump. The study is multicenter in France, prospective, randomized in two parallel groups 1:1, open-label, with a non-inferiority methodology versus a comparator device (Omnipod® pump marketed by the company Insulet and which is already reimbursed in France since 23/02/2016).

75 type 1 or 2 diabetic patients will be included in the study by 8 hospital centers specialized in diabetes.

In order to facilitate the recruitment of patients already using an Omnipod® pump who would be randomized to the Omnipod group (thus without changing their pump), it is proposed that these patients be able to use a Medtrum pump at the end of the study for one month. Thus all patients in the study will have the opportunity to use the new A7+ TouchCare® pump.

The duration of the study will be: 1 month of set-up, 3 months of patient recruitment, 12 weeks of follow-up per patient, 1 additional month for patients in the Omnipod group to test the Medtrum pump, 3 months of data management, i.e. approximately 11 months of study.

2.2 RATIONALE FOR THE STUDY DESIGN

The objectives of this study are to generate specific data on the use of the insulin pump model A7+ TouchCare® from MEDTRUM (CE marked medical device), to collect safety, tolerance and performance data.

3 MEDICAL DEVICE

3.1 IDENTIFICATION AND DESCRIPTION OF THE MEDICAL DEVICE OF THE STUDY

3.1.1 Mechanism of action of an insulin pump

The external insulin pump is a discreet device that continuously delivers small amounts of rapid insulin, thanks to a user-programmed and disconnectable external infusion device (catheter and tubing) to be changed regularly.

Thanks to the user's programming, the insulin pump reproduces what the body does naturally:

- Deliver small doses of rapid insulin at regular intervals (basal rate) throughout the day.
- Delivering an additional dose of insulin (bolus) at mealtime to cover carbohydrates absorbed at mealtime, during a snack or to correct hyperglycemia.

Thus, the insulin pump is an alternative to treatment with multiple insulin injections using pens and promotes better glycemic control.

Patch pumps are pumps without a catheter or external tubing that are attached directly to the skin with an adhesive.

The Medtrum A7+ TouchCare® Patch Pump as a stand-alone pump is designed for continuous subcutaneous delivery of insulin. The patch pump consists of two main components and three medical devices:

Insulin delivery unit

[figure not shown]
Pump base

Reservoir Patch

PDM

1. Bouton d'alimentation
2. Touche d'accueil
3. Port de chargement
4. Orifice de sortie de son
5. Voyant

✓ Gestionnaire Personnel de Diabète (FM-018)
(Personal Diabetes Manager, PDM)

1/ Insulin delivery unit is a combination of 2 devices:

- A durable part called the **pump base** which contains the electronics and stores the programming of the insulin delivery unit. It must be attached to the consumable, to the Reservoir-Patch, to allow insulin delivery.
- The **Patch Reservoirs** are the consumables. They are disposable and contain up to 200 units of rapid insulin. The reservoir of the A7+ device must be changed every 3 days.

It is the combination of these two elements that allows for the continuous delivery of insulin through a system without external tubing or catheters.

Then, to manage the pump, the patient will have to equip himself :

2/The remote control or **Personal Diabetes Manager (PDM)** has a color touch screen. The PDM allows programming and control of the pump (and continuous glucose monitoring system if applicable) via wireless radio frequency (RF) communication. The PDM also stores pump (and sensor) data for up to 90 days. The PDM is AC powered and does not require batteries.

The Medtrum A7+ TouchCare® pump (versus the Insulet Omnipod® pump) is a stand-alone component of a complete insulin management system. The system also provides interstitial fluid glucose measurement and the ability to set up hyper and hypoglycemia prevention alarms and predictive suspension of insulin delivery to avoid hypoglycemia.

It also provides patients with flexibility, including the ability to customize the insulin flow rate, or even reduce it to 0 units/hour, allowing it to be used in pediatrics in particular. In addition, the Medtrum A7+ TouchCare® pump comes with a cloud-based management system that can be operated from an app and laptop providing real-time information to caregivers and enabling remote patient monitoring.

Table 1. Administrative characteristics of the medical device under study

Name of the product under study	A7+ TouchCare® Insulin Pump
Indication	Insulin-dependent diabetes
Presentation / Composition	Permanent pump base associated with its consumable, the insulin patch reservoir (disposable) Individual remote control (PDM)
Class	Class IIB
Holder of the medical device	MEDTRUM
CE marking	19/02/2019

3.1.3 Procedure for using the device

Initial training for each center in the use of the Medtrum device will be conducted by an authorized representative of the manufacturer.

Medtrum is providing physicians with a data management system via an online portal to view data collected by the A7+ TouchCare® pump. Investigating centers will be able to extract data for study purposes (data reported on the eCRF), as they already do with data from an Omnipod® pump and an Abbott FreeStyle Libre sensor.

3.1.4 Possible adverse events related to the use of the device

Investigators should report any events that occur during the study (see Chapter 13).

Tolerance problems have already been reported with the patches of insulin sensors and pumps already on the market. These are essentially events of the type of local skin allergy at the location of the adhesive used to attach the pump.

Other side effects, the severity and appearance of which are not known at this time, may occur and will be reported during the study.

3.1.5 Packaging and labeling

Labels will be prepared in accordance with Good Manufacturing Practices (GMP) and clinical trial regulatory requirements to ensure complete traceability of device use from the beginning to the end of the study. Devices will be individually and uniquely numbered.

3.1.6 Conservation and storage

Study devices should be kept at room temperature, and in a secure location under appropriate storage conditions.

3.1.7 Supply of devices

The study devices will be provided by the sponsor and sent to each center (hospital pharmacist) who will acknowledge their receipt.

3.1.8 Randomization

Randomization will be performed using the eCRF provided to the investigators for the study. It will determine which arm the patient will be assigned to: either the "Omnipod" group (the patient will continue to use his current Omnipod pump) or the "Medtrum" group (the patient will have to switch to a Medtrum model).

3.1.9 Dispensing of devices

The study devices provided will be used only as specified in the study protocol. Study site personnel will be responsible for all devices delivered to the patient.

The date of dispensing, patient identification number, and lot number of the medical device should be recorded in the appropriate sections of the investigator record. The traceability label shall be retained in the investigator record or patient's medical record.

The investigator's medical team will provide initial training in the use of the pump for each patient and provide associated documentation.

Patients included in the study will already be users of the other devices used in the study (Omnipod® pump and FreeStyle blood glucose meter), and will use them in the study. No intervention on insulin and its administration is planned as part of the protocol.

3.1.10 Return of the devices

Unused study devices should not be discarded or used for any purpose other than this study. They should be kept in their original packaging.

The Clinical Research Associate (CRA) in charge of monitoring will collect the distribution forms for the medical devices under study at the end of the study and will verify all returns before making arrangements for direct repatriation to the Sponsor or its provider.

3.2 COMPLIANCE

The insulin treatment will be delivered by the pump, and the doses determined by the patient and injected by the pump are recorded by the device. This data can then be viewed and downloaded by the center using the online application provided by the manufacturer.

A measure of compliance with continuous glucose measurements by the patient will be collected using the data recorded in the FreeStyle Libre device.

3.3 EXPECTED SERIOUS ADVERSE EVENTS

As with any Class IIB medical device, risks associated with use cannot be excluded.

Each patient will already be using an Omnipod® insulin pump at the time of inclusion in the study. The use of another pump model (CE marked and already used in other countries) does not present any additional potential risk.

Any serious adverse event, whether or not related to the device under study or its use, must be reported in accordance with the instructions in Chapter 13.

3.4 OTHER DEVICES USED IN THE STUDY

In this study, in addition to the A7+ TouchCare® Medtrum pump, the patient will be given the following:

3.4.1 *FreeStyle Libre continuous glucose monitor*

The FreeStyle Libre meter is a Continuous Glucose Monitoring (CGM) system for patients with diabetes (Class IIb medical device). It displays glucose level data collected by the associated sensor that measures glucose levels in the interstitial fluid. Unlike existing CGMs on the market, the FreeStyle Libre uses NFC technology and requires the sensor to be scanned regularly for continuous glucose readings.

It records and stores up to 90 days of glucose data. To obtain a complete view of glucose levels over the past 3 months, the sensor must be replaced every 14 days and scanned by the patient at least once every 8 hours. The sensor should be removed before undergoing an MRI.

The functions of this player are as follows:

- Continuous glucose measurement on the interstitial liquid thanks to a sensor placed on the epidermis with the help of an adhesive base (maximum 14 days of use)
- Data display on a Reader (Wireless handheld terminal) for patient viewing. The FreeStyle LibreLink application is also available as a medical device to replace the FreeStyle Libre reader. It is possible to scan the FreeStyle Libre sensor using either the LibreLink app on Android or iOS, or the FreeStyle Libre reader, or both.
- Data from the system can be downloaded to a computer and then transmitted to the manufacturer's cloud so that the physician can view the information

Abbott is providing physicians with an online application to view the data collected by the FreeStyle Libre reader. Investigating centers already equipped with this software will be able to extract the data for the study (data to be reported on the eCRF).

3.4.2 *Insulet Omnipod® Patch Pump (comparator device)*

This medical device consists of a small pump that is glued directly to the skin and insulin is delivered into the subcutaneous tissue through a cannula that penetrates the skin when the pump is primed. Insulin is injected directly into the pump's built-in reservoir (no separate reservoir).

The pump must be removed when it is empty, at most every 3 days, and disposed of, a new one being put in place for the continuation of the treatment. It is therefore a single-use pump.

The pump has a Personal *Diabetes Manager* (PDM) with a non-touch screen. The PDM controls the pump and delivers insulin continuously (wireless radio frequency transmission). It allows you to record data for the previous 90 days.

3.4.3 Centralization of information sources and identification keys

The clinical database of the study will be managed exclusively by the provider in charge of the study logistics (Axonal-Biostatem). This database will not contain any directly nominative data.

[figure not shown]
The provider provides the centers with an electronic observation book (e-CRF) accessible via the Internet. Each user is identified by a personal and unique login/password.

The identifiers for each patient according to the different data sources are as follows:

- **Pump-ID:** number of the pump kit given to the patient. This ID will be entered into the clinical database in the format | __ | __ | __ | .
- **ID-eCRF:** unique patient identifier for the study in the clinical database (eCRF) on the format center no. - patient no. in the format | __ | - | __ | __ | .

The centers will also use applications accessible via the Internet, made available by the manufacturers to visualize and exploit the data recorded and transmitted by the various devices used (pump, blood glucose meter).

For example, the data is returned to the physician in the form of graphs, tables and calculated average values. Physicians will thus be able to have, for each patient, the average blood glucose levels over the defined periods, the estimated A1C, the % of time in range, etc.

These applications are used routinely in the centers. Only the application provided by Medtrum for its pump data will require specific training for the centers. Investigators will need to report these calculated variables in the eCRF to populate the clinical database of the study.

4 OBJECTIVES OF THE STUDY

4.1 MAIN OBJECTIVE

The primary endpoint was estimated HbA1c based on mean blood glucose measurements over the past 10 weeks for each pump use.

The patient's average blood glucose over the past 10 weeks will be calculated in each arm from measurements automatically recorded by a FreeStyleLibre sensor, which the patient is already using.

4.2 SECONDARY OBJECTIVES

The secondary objectives are to describe the following information:

- HbA1c values measured at the medical and biological laboratory at the beginning and end of the study
- Glucose measurements (minimum, maximum, mean/median, standard deviation, off-target value, time in range[Time in Range] , variability)
- Glycemic events (hypoglycemia and hyperglycemia - as defined by the ADA²⁵ , coma, other complications)
- Skin and general tolerance
- Technical incidents with the device
- Overall patient satisfaction, on the overall population, in each arm and comparison between the two arms
- Insulin treatment compliance

5 PATIENT SELECTION

The investigating centers will propose participation in the study for each patient potentially eligible for the study according to the inclusion and non-inclusion criteria.

Each patient must be informed orally and in writing by the investigator by means of the information leaflet informing them of the objectives and methods of the study, of the collection and computer processing of their health data, and of their right to withdraw from the study without having to justify themselves. The patient will have the opportunity to ask questions to the study personnel of the investigating center. If a patient decides to

participate, he or she must knowingly sign the consent form approved by the Ethics Committee before any study-related procedure.

A patient will only be included in the clinical study after he or she has given written informed consent and met all inclusion criteria and none of the non-inclusion criteria.

As the patients in this study are not involved in emergency medical treatment, no consent will be collected in this specific emergency setting.

6 STUDY POPULATION

6.1 INCLUSION CRITERIA

To be included in the study, all patients must meet all of the following inclusion criteria:

1. Patient with type 1 or type 2 diabetes, 18 years of age and older
2. Patient already equipped with an Omnipod® insulin patch pump (Insulet) and a FreeStyleLibre sensor (Abbott).
3. A1C between $\geq 6.5\%$ - ≤ 9.5
4. Treated with any type of rapid-acting insulin except FIASP (which can be substituted as needed) with 60 IU maximum per day (no use of insulin supplements by pen injector allowed).
5. Patient able to receive and understand study information, give written informed consent, and readily participate in the study.

6.2 NON-INCLUSION CRITERIA

Patients will not participate in this clinical study if they **meet at least one of the following criteria**:

1. Patient already participating in another study
2. Patient under the protection of the court or under guardianship or curatorship
3. Type 2 diabetic patient requiring a daily dose of insulin greater than 60 IU per day
4. Patients unable to continue using an insulin pump for reasons such as: severe psychiatric disorders, rapid progression of ischemic or proliferative retinopathy prior to laser treatment, exposure to magnetic fields)
5. Patient allergic to nickel or adhesive
6. Patient not affiliated to a social security system
7. Pregnant and breastfeeding women
8. Or any other criteria as determined by the investigator.

6.3 PROHIBITED TREATMENTS

Investigators are free to manage their patients with diabetes as usual, but any treatment should be documented during the study, as well as any changes in treatment during the study. Therefore, there are no prohibited treatments during the study.

6.4 CRITERIA FOR PREMATURE PATIENT DISCHARGE FROM THE STUDY

Patients may be prematurely withdrawn from the study in the following situations:

- Inclusion found not to be in compliance with the protocol

- Patient decision: the patient is free at any time to withdraw from the study without prejudice to the quality of subsequent care
- Malfunction of a medical device that does not allow the study to continue or does not allow data to be collected reliably
- Any clinical reason given by the investigator
- Patient lost to follow-up.

If a patient withdraws prematurely from the study due to a specific stopping criterion, the reason and date of withdrawal should be reported in the case report book.

Any adverse events should be reported and documented according to the detailed instructions in Chapter 13.

6.5 REPLACEMENTS

Patients who leave the study will not be replaced.

If dropouts significantly affect the number of patients in the study, the Scientific Committee will be asked to make any useful decision, such as additional inclusions.

7 SCHEDULE OF VISITS AND STUDY PROCEDURES

7.1 SCHEDULE OF VISITS

For this study, the following visits or contacts will be made for each patient by the investigators:

- Visit 1 (D0): Inclusion visit with collection of informed consent and randomization of the type of pump to be used.
- Visit 2 (V2) 4 weeks later : Follow-up visit after 4 weeks of pump use
- Visit 3 (V3) 12 weeks after inclusion: End of study visit and measurement of the primary endpoint
- An additional month for patients in the Omnipod group to use the Medtrum pump (considered to facilitate participation in the study for patients who would be randomized to the comparator group)

7.2 EVALUATION SCHEDULE

The evaluation schedule is presented below in **Table 2**.

	screening	inclusion	1M	3M	1M additional
					Omnipod patients only
seeking patients already using Insulet + FreeStyle Libre	X				
ensure availability of HbA1c <1M and blood glucose results	X				
informing the patient		X			
signature consent		X			
verification of inclusion and exclusion criteria		X			
randomisation of pump type		X			
socio-demographic data		X			
history of the disease		X			
HbA1c values and A1c estimates at inclusion		X			
major blood glucose events last month and last 6 months		X			
supply of MEDTRUM equipment		X			X
verification of the correct use of devices		X	X	X	
possible incidents with the devices			X	X	X
adverse events			X	X	X
collection and reporting of blood glucose data and events		X	X	X	X
collection and reporting of pump data			X	X	X
pump and PDM satisfaction questionnaire		P	P	P	P
P = questionnaire filled in by the patient					

Table 2 Evaluation Schedule

7.3 VISIT 1: INCLUSION VISIT WITH INFORMED CONSENT

No study-specific procedures should be performed until informed consent has been obtained from the patient.

Study procedures at Visit 1 include the following assessments:

- Provide verbal information about the study procedures and objectives as well as those presented in the package insert, and ensure that the patient has the opportunity to ask questions
- Obtaining the signature of the informed consent
- Collect the following data using the eCRF:
 - Socio-demographic data
 - Age of diabetes, type, age of insulin therapy
 - HbA1C at the time of insulin pump prescription
 - Current model of pump used by the patient
 - Patient satisfaction with the current pump
 - Type of insulin used
 - Last HbA1C value less than one month old
 - Available glucose measurements (average of glucose measurements, estimated HbA1c, time in range)
 - Number of major glycemic events in the past month (as defined by the ADA) and in the past 6 months
 - Randomization of the patient in the pump group "Omnipod" or "Medtrum"

7.4 VISIT 2 (4 WEEKS): FOLLOW-UP VISIT AFTER 4 WEEKS OF PUMP USE.

- Collect tolerance data and possible adverse events, and report them as required from the eCRF
- Verify the conditions of use of the devices by the patient

- Collect time-stamped records of glucose values (as well as HbA1c estimated from average glucose measurements) and glycemic events, hypoglycemia and hyperglycemia, and insulin doses administered, from software provided by manufacturers
- Collect technical incidents with the device (catheter occlusion, alarms, pump detachment, pain, allergy, etc.)
- Patient satisfaction with their insulin delivery system
- Confirm or schedule the date of the V3 visit after 3 months of use
- Record all relevant data in the eCRF.

7.5 VISIT 3 (12 WEEKS): END OF STUDY VISIT

- Collect tolerance data and possible adverse events, and report them as required from the eCRF
- Verify the conditions of use of the devices by the patient
- Collect time-stamped records of glucose values (as well as HbA1c estimated from average glucose measurements) and glycemic events, hypoglycemia and hyperglycemia, insulin doses administered
- Collect technical incidents with the device (catheter occlusion, alarms, pump detachment, pain, allergy, etc.)
- Collect patient satisfaction and preference for either pump used (for Medtrum patients only)
- Recovering Medtrum materials
- Record all relevant data in the eCRF
- Offer the patient, if he is in the "Omnipod" group, to use a Medtrum pump for one month and make an appointment in one month for an end-of-study and material recovery visit

7.6 VISIT 4 (4 WEEKS AFTER THE END OF THE STUDY): AFTER 1 MONTH OF USE OF THE MEDTRUM PUMP (ONLY PATIENTS RANDOMIZED IN THE OMNIPOD GROUP)

- Collect tolerance data and possible adverse events, and report them as required from the eCRF
- Collect time-stamped records of glucose values (as well as HbA1c estimated from average glucose measurements) and glycemic events, hypoglycemia and hyperglycemia, insulin doses administered
- Collect technical incidents with the device (catheter occlusion, alarms, pump detachment, pain, allergy, etc.)
- Gather patient satisfaction and preference for either pump used
- Recovering Medtrum materials
- Record all relevant data in the eCRF

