Objectives	
 ● Main Objective: The primary endpoint is the estimate of HbA1c based on the mean of continuous glucose measurements obtained over the past 10 weeks for each pump use. 
The patient's glucose level (averaged over 10 weeks in each arm) will be calculated from measurements automatically recorded by a Continuous Glucose Measurement sensor that the patient already uses: the FreeStyle Libre (Abbott).
 
 ● Secondary Objectives: 
 ○ HbA1c values measured at the medical and biological laboratory at the beginning and end of the study ○ Glucose measurements (minimum, maximum, mean/median, standard deviation, out-of-range value, time in range[Time in Range] , variability) ○ Glycemic events (hypo- and hyperglycemia - as defined by the ADA, coma, other complications) ○ Skin and general tolerance ○ Technical incidents with the device

	
 ○ Overall patient satisfaction, out of the total study population, in each arm and the comparison between the two arms ○ Insulin treatment compliance
Study population	Type 1 or 2 diabetic patients already equipped with an Omnipod® insulin patch pump (Insulet) and a FreeStyleLibre® blood glucose sensor (Abbott).
Number of patients	75 diabetic patients (type 1 & 2) recruited in 3 months.
Duration of follow-up per patient	3 months from randomization. Follow-up visits at 4 weeks and 12 weeks. Patients randomized to the control arm (Omnipod) will be allowed to use an A7+Touchcare® pump for 1 full month after the 3-month visit if they wish, to facilitate recruitment by the centers and to allow for a satisfaction measure for both pumps.
Number of centers	8 centers in France (CHU and CHG).

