- Description of local skin tolerance at the pump site and at the FreeStyle Libre blood glucose sensor site).
- Description of any local or systemic safety issues reported during the study, including the additional one-month phase at the end of the study for patients in the "Omnipod" arm
- Description in the total population, in each group and comparison between groups of the number of patients who had at least one tolerance problem.

❖ **Incidents with devices**

- Description of any type of incident involving the operation of the medical devices used, particularly for pumps: pulling out, control problems, transmission difficulties, obstructions, leaks, etc.
- Description in each group, in the overall population and comparison between groups

❖ Patient satisfaction

- Description of the responses to the self-questionnaire assessing satisfaction with the use of the device (pump+PDM), in each group and in the total population
- Comparison of responses between groups
- Description of responses to the final question regarding patient preference between the Medtrum device and the Omnipod device: in each group and in the total population

❖ Insulin treatment

- Description of insulin doses delivered
- Description of any additional insulin injections with a pen during the study
- Description in the total population, in each group and comparison between groups

11.2.5 Tolerance analyses:

The analyses will be performed on the tolerance population.

Prior to any analysis all DM-related incidents and DM-related tolerance will be coded by the MedDRA regulatory medical dictionary (version 20.0 or later).

A summary table (number and percentage of patients with an AE and number of events) by organ system class (OSG) and preferred term (PT) will be presented for the following categories of events by dissociating DM-related incidents and tolerance:

- According to the link (device AND procedure),
- Depending on the link (device OR procedure),
- Depending on the severity,
- Depending on the actions taken (de-pairing).

A listing of individual data will be provided describing all the information collected via the eCRF concerning the IS (including duration, resolution, severity criteria, linkage, severity etc.)

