7.4.2 Secondary endpoint analyses

Analyses will be performed on the ITTm population.

Each variable will be described globally and by pump group.

The secondary endpoints are:

1. HbA1c

The evolution of HbA1c (measured in the laboratory) between D0 and 3M will be described, and a comparison between the groups will be made using a Student's t test or a Mann and Whitney test.

2. Glucose level measurement

The mean blood glucose level and its standard deviation (Blood Glucose Deviation SD) will be described over each period (between V1 and V2, then between V2 and v3, then between V3 and V4) and over the total duration of the study (mean, median, standard deviation, Q1-Q3, minimum and maximum). The coefficient of variation of glucose values will also be described.

The evolution of the average blood glucose level compared to baseline will be described at each visit.

FSL wear time (%) will be described.

The % of blood glucose values spent in target (time in range: [70; 180]), hypoglycemia (<70mg/dl), and hyperglycemia (>180 mg/dl) will be described over each time period in each pump group and in the total population.

For these criteria, comparisons between groups will be made using the Student or Mann-Whitney test.

3. Glycemic events

The number of hypoglycemic events will be described overall and in each period by severity level (according to ADA consensus definitions) overall and in each pump group.

Comparisons between groups will be made using Student or Mann-Whitney tests.

The % of time spent in hyperglycemia will be described overall and over each period and in each pump group. Comparisons between groups will be made using Student's t test or Mann and Whitney test.

4. Device tolerance

The analysis of this criterion is detailed in section 7.4 of this document.

5. Incidents with devices

The following criteria will be described for each period and by pump group (after reclassification):

- Pump occlusion (yes; no)
 - If yes, number of times
- Pump detachment (yes; no)
 - If yes, number of times
- Complete stop / breakage of the pump (yes; no)
 - If yes, number of times
- Other pump malfunction (yes; no)
 - All other possible malfunctions will be listed.

6. Patient satisfaction

The following criteria will be described for each period and by pump group:

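### Pump preference should not be pooled over the total population: the two arms answer at different visits and exposures, and Omnipod-arm patients answer only if they chose to try the Medtrum pump.

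*Protocol*

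**What the plan says.** **When preference is asked.** At visit 3, after 12 weeks, Protocol 7.5 asks sites to "Collect patient satisfaction and preference for either pump used (for Medtrum patients only"). For the other arm the question comes at visit 4, under a heading that reads "AFTER 1 MONTH OF USE OF THE MEDTRUM PUMP (ONLY PATIENTS RANDOMIZED IN THE OMNIPOD GROUP"), where sites are to "Gather patient satisfaction and preference for either pump used" (Protocol 7.6).

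**Who reaches visit 4.** The extra month is voluntary. The protocol summary, under duration of follow-up, says control patients "will be allowed to use an A7+Touchcare® pump for 1 full month after the 3-month visit if they wish". Protocol 7.5 likewise describes an offer made at visit 3. No preference question is scheduled for an Omnipod-arm patient who declines.

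**How it is summarised.** Protocol 11.2.4 describes answers to the final question "regarding patient preference between the Medtrum device and the Omnipod device: in each group and in the total population". SAP 7.4.2 opens with the rule "Each variable will be described globally and by pump group", and the SAP section 8 templates carry a Total column. Item 6 of SAP 7.4.2, which covers satisfaction and preference, mentions only periods and pump groups. SAP section 6 declares no change from the protocol's analyses.

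**Missing answers.** SAP 5.2 reports the number of missing values but computes percentages without them. Secondary endpoints use the ITTm population, which is the ITT population less four patients discharged because of COVID-19 (SAP 7.1.3 and 7.4.2).

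**The concern.** A percentage labelled as the total population reads as the view of the randomised patients. This one would be the view of the Medtrum-arm patients who answered at 12 weeks plus the Omnipod-arm patients who volunteered for a month on the new pump. The two parts differ in length of exposure, and the second is self-selected. Patients content with Omnipod have the least reason to try another pump, so those who decline may well be less favourable to Medtrum than those who accept.

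The trial is open-label and preference is listed within a secondary endpoint, so a single pooled figure is easily taken at face value. What is at stake is the reading of that descriptive figure. No test is attached to preference, and nothing here touches the non-inferiority analysis.

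**Working it through.** The plan states no uptake and no preference rate, so there is no plan figure to reproduce. The check is algebra with assumed rates.

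**Inputs.** Allocation is 1:1 (Protocol 2.1), so I take equal arms. For simplicity I take every Medtrum-arm patient as answering at visit 3 and every trier as answering at visit 4. Let
- u = share of the Omnipod arm that takes the optional month
- pM = share preferring Medtrum in the Medtrum arm
- p1 = the same share among Omnipod-arm triers
- p0 = the same share among decliners, had they tried the pump.

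All four are assumptions.

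**Formulas.**
- Pooled percentage as the rules would produce it: R = (pM + u·p1)/(1 + u)
- Pooled percentage had everyone answered: F = (pM + u·p1 + (1 − u)·p0)/2
- Pooled bias: R − F = (1 − u)/2 × (R − p0)
- Omnipod-arm bias: p1 − [u·p1 + (1 − u)·p0] = (1 − u)(p1 − p0)
- Medtrum arm's share of respondents: 1/(1 + u)

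**Weights.** The last line needs no view about decliners. The Medtrum arm supplies 1/1.8 = 55.6% of answers at 80% uptake and 1/1.4 = 71.4% at 40%, against 50% by design.

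**Illustration with pM = 0.50, p1 = 0.60, p0 = 0.30.**

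| Uptake u | R | F | Pooled bias (points) | Omnipod-arm bias (points) |
|---|---|---|---|---|
| 1.0 | 0.550 | 0.550 | 0 | 0 |
| 0.9 | 0.547 | 0.535 | +1.2 | +3 |
| 0.8 | 0.544 | 0.520 | +2.4 | +6 |
| 0.6 | 0.537 | 0.490 | +4.7 | +12 |
| 0.4 | 0.529 | 0.460 | +6.9 | +18 |

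For u = 0.8: R = (0.50 + 0.48)/1.8 = 0.544; F = (0.50 + 0.48 + 0.06)/2 = 0.520; the Omnipod arm reads 0.60 against 0.48 + 0.06 = 0.54.

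**Sign.** The pooled bias favours Medtrum only if p0 is below R.
- With all three rates at 0.50 it is zero at any uptake.
- With pM = 0.30, p1 = 0.50, p0 = 0.40 it is −0.1, −0.5 and −1.3 points at u = 0.8, 0.6 and 0.4.

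**Bounds.** If the pooled percentage came out at 50%, letting p0 run from 0 to 1 puts the bias within ±(1 − u)/2 × 50 points: ±5 at 80% uptake and ±15 at 40%.

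**The case against.** Several points on the other side have force.

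- **The SAP's own preference item does not pool.** Item 6 asks for results by period and pump group, which already separates Medtrum at visit 3 from Omnipod at visit 4. This is right as far as it goes. But the general rule of the same section, the Total column and Protocol 11.2.4 all still call for a total, and SAP section 6 declares no departure from the protocol. By-group display also leaves the selection inside the Omnipod arm, where it is larger than in the pooled figure.
- **Non-response is not hidden.** SAP 5.2 and the templates show missing counts by group. This stands. What is lacking is a separation of patients who declined the pump from patients who tried it and did not answer.
- **Decliners have no comparative preference.** Every patient enters on Omnipod, so all respondents have used both pumps, and a percentage among those who tried both is a legitimate target. This also stands, and it is why decliners should not be forced into the only denominator.
- **Uptake may be high.** The protocol presents the extra month as a recruitment incentive. It may be, and with full uptake the selection disappears, though the difference in exposure does not.

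A reader might infer that the pooled figure is biased in the sponsor's favour. The documents do not support that as a fact: they give no uptake, no preference rates and no reasons for declining, and the sign can reverse. A reader might also count every decliner as not preferring Medtrum. With pM = 0.50 and p1 = 0.60 that gives pooled biases of +5.4 points at 80% uptake and +15.9 at 40%, but it is the extreme case (p0 = 0), not an estimate.

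**Conclusion.** The structural point holds on the documents alone. As the rules are written, the total-population preference figure mixes 12-week and one-month exposure to the Medtrum pump, over-weights the Medtrum arm whenever uptake is incomplete, and leaves decliners out. Bias is possible and probably towards Medtrum, but neither its direction nor its size is established. Under the one set of assumed rates tabulated above it runs from zero at full uptake to about +7 points pooled and +18 points in the Omnipod arm at 40% uptake. This is a minor improvement to a descriptive item, with no bearing on the primary endpoint.

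**What to change.** In Protocol 11.2.4, exempt preference from the total-population description. In SAP 7.4.2, exempt it from the general global-and-by-group rule and from the Total column. Report it by arm and visit only, Medtrum at visit 3 and Omnipod at visit 4, as item 6 is already worded.

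For the Omnipod arm, state the numbers offered the extra month, accepting it and answering, with decliners and non-responders as separate categories. Give the percentage twice: among those who tried both pumps, and over the full arm in the ITTm population. Acceptance should be derivable from the visit 4 records and from the supply of Medtrum equipment scheduled for the additional month in Protocol Table 2. The number offered may have to be confirmed with the sites.

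The cost is a few lines of wording, a slightly longer table and the loss of a single headline preference figure.
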